(1) Resuscitation requiring early intubation according to the American Academy of Pediatrics guidelines for neonatal resuscitation [8]; (2)major congenital malformations or known complex congenital heart disease; (3)pulmonary hemorrhage or pneumothorax; (4) congenital lung diseases or malformations or pulmonary hypoplasia;

Setting

We plan to enroll preterm infants born between 26 and 34 weeks of gestational age from 18 tertiary NICUs in China. These 18 tertiary NICUs have more than 800 NICU beds and annual admissions of nearly 8,000 preterm infants with RDS each year. The first (XZ) and last authors (RR) take responsibility for the accuracy and completeness

of the trial.

Randomization

To avoid the chance of having more infants in one group than another, block randomization will be applied, with a block size of 4. The envelopes are sealed, shuffled, and then numbered in sequential order from 1 to 4. A clinician who is not in the trial group will open the envelope and randomize patients. This procedure will be repeated for each group of four infants. Infants will be stratified according to 26^{0/7}-27^{6/7} weeks, 28^{0/7}-29^{6/7} weeks, 30^{0/7}-31^{6/7} weeks and 32^{0/7}-33^{6/7} weeks. Infants born from multiple gestations will be assigned by individual randomization. Infants randomized to one arm cannot crossover to the other or vice-versa during the study.

Trial intervention

Ventilators

CPAP: CPAP will be provided by continuous flow devices (CNO Medin, Germany or Carefusion, USA) Bubble CPAP devices will not be used.

NHFOV: NHFOV will be provided by two ventilators (CNO, Medin, Germany or SLE 5000, UK). The Medin CNC ventilator produces high-frequency oscillations by flow interruption with cyclic opening-closure of the end expiratory valve. Otherwise, The SLE 5000 ventilator is a time-cycled, pressure-limited and continuous-flow neonatal ventilator.

Before the beginning of the study all ventilators will be checked to ensure that there is no malfunction.

Interfaces

CPAP and NHFOV will be all administered through short, low-resistance binasal prongs,

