The primary outcome of this trial will be to determine the need for IMV in the first 7 days of life in preterm infants randomized to the two groups. Secondary outcomes include days of hospitalization, days on noninvasive ventilation, days on supplemental oxygen, pre-discharge mortality, surfactant doses, incidence of stage III ROP and BPD, occurrences of abdominal distention, air leaks, IVH \geq grade 3 and NEC. Secondary outcomes also include Bayley Scales of Infant Development at 18-24 months of corrected age. BPD will be defined according to the National Institutes of Health consensus definition as mild, moderate and severe BPD [12], IVH classification according to Papile et al [13] and for NEC, Bell staging will be used [14].

Data collection

Patient demographic data include: sex, birth weight, gestational age, Apgar scores, mode of

delivery, prenatal corticosteroid use, premature rupture of the membrane, RDS Silverman score and critical risk index for babies-II (CRIB-II) score. More details see in the appendix Clinical data :Including the need for IMV, days of hospitalization, days on noninvasive respiratory support, days on supplemental oxygen, mortality, the need for surfactant, occurrences of abdominal distention, air leaks, IVH \geq grade and NEC \geq stage II. More details see in the appendix Follow-up data: The incidence of BPD and ROP at a post-menstrual age of 36 weeks or at discharge, and Bayley Scales of Infant Development at 18-24 months of corrected age.

Sample size calculation

It is difficult to calculate a sample size for such a study, since it is the first to investigate NHFOV vs CPAP in primary support phase in preterm infants with RDS. There is only one preliminary study available about the primary outcome “need for IMV”. This pilot study conducted by Zhu et al provides data about the primary outcome “need for IMV”. This trial showed the need for IMV was significantly lower in the NHFOV compared with the NCPAP group (24.3% vs. 56.4%, $P < 0.01$). Considering an α -error of 0.05 and a power of 90%, 150 neonates should be enrolled in each arm (with a 1:1 design) to detect the same difference.

Statistical methods

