Data will be analyzed using SPSS version 19 software. The statistical analyses include Student's t-test for continuous data and compared proportions using Chi-squared test, and Fisher's exact test for categorical data. Predefined four subgroups are 26^{0/7}-27^{6/7} weeks, 28^{0/7}-29^{6/7} weeks, 30^{0/7}-31^{6/7} weeks and 32^{0/7}-33^{6/7} weeks, and subgroup analyses will be conducted for the primary outcome in the preterm infants. To further evaluate the effect of NHFOV on intubation within

subgroup, the test of treatment-by-gestational age subgroup interaction will also be done using the paired binary logistic regression. For the preterm infants lost to follow-up, the missing values of the primary and secondary outcomes are replaced using multiple imputation. A P -value < 0.05 will be regarded as statistically significant.

Data Safety Monitoring Board (DSMB): [name], Professor of Pediatrics, Oklahoma University Medical Center, Oklahoma, [name], Professor of Pediatrics, Medical College of Georgia, Georgia Health Sciences University, Augusta, Georgia, and [name], MD., MPH (Biostatistics and Epidemiology) Assistant Professor of Pediatrics, Keck School of Medicine of the University of Southern California, Los Angeles, California will serve as DSMB members. [name] will also serve as consultant for statistical analysis.

Registration number

The trial has been approved by the centralized ethics committee (The Ethics Committee of Daping Hospital, Research Institute of Surgery, Third Military Medical University) and registered at <http://www.clinicaltrials.gov>(ID: NCT03099694).

Discussion

In the past decades, several clinical trials have compared the effects between NHFOV and NCPAP in neonates as a rescue mode or during weaning from IMV. These trials demonstrated that NHFOV applied with nasopharyngeal tube are more beneficial than NCPAP in reducing CO₂ levels [16-19]. Recently, two retrospective case series also reported NHFOV could be applied in preterm infants as a rescue treatment after the

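### Siblings are randomized individually within gestational-age strata but analysed as unrelated infants: error rates hold, and the cost is a modest loss of precision

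*Combined protocol and SAP*

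**What the plan says.** All references are to the combined protocol and SAP.

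- **Randomization.** The section says "block randomization will be applied, with a block size of 4", with stratification into four two-week gestational-age bands from 26 to 33 completed weeks. On siblings it says "Infants born from multiple gestations will be assigned by individual randomization".
- **Outcomes.** The primary outcome is binary: "the need for IMV in the first 7 days of life in preterm infants randomized to the two groups". Secondary outcomes include continuous ones, such as days in hospital, days on oxygen and Bayley scores.
- **Statistical methods.** The main comparisons use a "t-test for continuous data and compared proportions using Chi-squared test", plus Fisher's exact test. The section has no family term, no stratum term in the main comparison, and no sensitivity analysis for multiples. The word paired appears once, for the treatment-by-gestational-age test: the "interaction will also be done using the paired binary logistic regression". What is paired is not defined.
- **Sample size calculation.** It plans 150 infants per arm for 56.4% versus 24.3% at 90% power. Multiples are not mentioned.
- **Data collection.** The items named include neither plurality nor a mother identifier. The section refers to an appendix for more detail, and no case report form is shown.

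**The concern.** The listed tests assume that one infant's outcome says nothing about another's. Siblings share a mother, a gestational age and a delivery, so their outcomes are likely to be correlated. Sharing a gestational age also puts them in the same stratum, and siblings entered one after the other often fall in the same block of 4. That pushes them towards opposite arms, where they form natural matched pairs. A test that ignores this reports a variance that is not quite right and leaves the within-pair comparison unused. It likewise leaves unused the strata on which the allocation was balanced. At stake are the width of the reported intervals and the efficiency of the comparison.

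**Working it through.** **The plan's own figure.** The documents give no figure for siblings. The nearest is 150 per arm. For 56.4% versus 24.3%, two-sided 0.05 and 90% power, the standard formula with pooled variance under the null gives 47 per arm (54 with continuity correction), so 150 is not reproduced. That mismatch is a separate matter. Here it matters only because 150 per arm gives about 99.996% power for that difference.

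**Inputs.**
- From the documents: individual allocation of siblings, blocks of 4, gestational-age strata, the two event rates, and 150 per arm.
- Assumed: f, the share of enrolled infants who belong to an enrolled twin pair, 0.2–0.3; ρ, the sibling correlation, 0.2–0.5; twins entered consecutively on one list.

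**Step 1: chance of opposite arms.** If the first twin takes place 1, 2 or 3 in a block, the second is in the same block and takes the other arm with probability 2/3. If the first takes place 4, the second opens a new block, with probability 1/2.

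3/4 × 2/3 + 1/4 × 1/2 = 0.625.

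**Step 2: error in the unadjusted variance, no treatment effect.** True/nominal variance = 1 + fρ(1 − 2 × 0.625) = 1 − 0.25fρ.

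**Step 3: information in an analysis that weights by the correlation, relative to the nominal variance.** Ratio = (1 − f) + f[0.625/(1 − ρ) + 0.375/(1 + ρ)].

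**Step 4: real gain.** The fair comparator is the variance that the unadjusted estimator actually has, so the ratios from steps 2 and 3 are multiplied.

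| f | ρ | Step 2 | Step 3 | Product |
|---|---|---|---|---|
| 0.2 | 0.2 | 0.990 | 1.019 | 1.009 |
| 0.3 | 0.2 | 0.985 | 1.028 | 1.013 |
| 0.2 | 0.5 | 0.975 | 1.100 | 1.073 |
| 0.3 | 0.5 | 0.9625 | 1.150 | 1.107 |

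The unadjusted variance is 1–4% too large. On the standard-error scale, √0.990 = 0.995 and √0.9625 = 0.981, an error of 0.5–2%. The gain in effective sample size is 0.9–10.7%.

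**Step 5: if entry is not consecutive.** With a 50:50 split, step 2 gives 1.00, so the unadjusted variance is right under the null. Step 3 with 0.5 in place of both 0.625 and 0.375 gives 1.008 (f = 0.2, ρ = 0.2) to 1.100 (f = 0.3, ρ = 0.5). A gain of 1–10% remains.

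**Step 6: type I error.** Simulations of 300 infants with f = 0.2–0.4 and ρ = 0.3–0.7 (8,000 runs each, Monte Carlo error about 0.24 points) gave 4.4–5.2% with blocks of 4 and 4.8–5.1% with simple randomization.

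**Step 7: power at the planned difference.** Take an extreme case in which all siblings share an arm, f = 0.4 and ρ = 0.7. The design effect is 1 + 0.4 × 0.7 = 1.28, and power is still 99.94%.

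**Step 8: ceiling on ρ for the primary outcome.** For opposite-arm siblings with risks 24.3% and 56.4%, the largest possible correlation is √[(0.243 × 0.436)/(0.757 × 0.564)] = 0.498. The upper assumed value of 0.5 therefore sits at the limit.

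**Step 9: outcomes with higher correlation.** With f = 0.1–0.4 and the 0.625 split, the actual standard error falls by 1.8–6.3% at ρ = 0.5 and by 5.1–15.9% at ρ = 0.7.

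**The case against.** The strongest case against is that the planned tests are valid, so GEE is a refinement and not a correction. Much of this stands.

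- **False positives.** A reader might infer that ignoring siblings inflates type I error. It does not: individual allocation puts about half or more of twin pairs in opposite arms, so the covariances cancel or make the test slightly conservative.
- **Power.** A reader might infer that the trial loses useful power. The only effect that the documents plan for is 56.4 − 24.3 = 32.1 points, where power exceeds 99.9% either way. A smaller target would have to come from outside the documents.
- **Size of the gain.** Step 3 alone suggests 2–15%. That compares with the nominal variance, which is itself 1–4% too large, so it overstates the gain.
- **Direction.** A reader might infer that the interval is always too wide. That holds under no effect with consecutive entry. Under the planned effect, simulated ratios of true to unadjusted standard error were 0.97–1.05 in one set (3,000 runs, Monte Carlo error about 1.3%) and 0.98–1.00 in a larger one (10,000 runs). The direction is not settled there.
- **Inputs.** f and ρ are assumed, and the protocol does not say that siblings enter consecutively. Each sibling must qualify separately (for example, Silverman score above 5), so some pairs will contribute one infant. Adjusting for gestational-age stratum also removes part of the correlation.
- **Identifier.** It cannot be said that a mother identifier is not collected, because the full data form is not shown.

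None of this shows that the plan handles siblings. The paired regression is confined to the interaction test and its pairing is undefined, so it does not cover the main comparisons.

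**Conclusion.** The point holds as a low-cost improvement. Siblings are randomized individually within strata, and neither the family nor the strata enter the primary or secondary comparisons. The primary conclusion is not at risk.

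The 1–4% variance error and the 1–11% gain rest on the assumed share of multiples, the assumed correlation and, for the variance error, consecutive entry. For the primary outcome the low end is more likely, because of stratum adjustment and the correlation ceiling. The gain could be larger for secondary outcomes with high sibling correlation, such as Bayley scores, but the documents give no figure from which to show that.

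**What to change.** In Statistical methods:

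- Analyse the primary outcome by logistic regression adjusted for the four randomization strata, fitted by GEE with mother as the cluster, an exchangeable working correlation and robust standard errors.
- Use the same clustering for the secondary outcomes.
- Say what is paired in the interaction model, or remove the word.

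In Data collection, record a mother or pregnancy identifier, or confirm that the data form already has one. This is easier at enrolment than afterwards across 18 centres.

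**Cost.** SAP wording, slightly more analysis work and at most one data field. Allocation and sample size do not change. The primary estimate becomes a covariate-adjusted odds ratio; a risk difference can be reported beside it. With 20–30% of 300 infants in pairs there would be 30–45 pairs and 300 − 45 = 255 to 300 − 30 = 270 families, which is ample for a robust standard error.

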since these are supposed to be the best in terms of resistive charge, leaks and/of comfort. Nasal prongs size will be chosen according to the nares' diameter as the best fitting ones (the largest ones that fit the nares without blanching the surrounding tissues) and following manufacturer's recommendations. Particular care (e.g.: pacifiers, positioning, nursing) will be applied to reduce leaks and improve patients' comfort. These matters will be evaluated through a dedicated 30 min observation period when study intervention will be instigated.

Ventilatory management

The two different respiratory supports will be managed as follows:

CPAP: Neonates assigned to the CPAP group were initiated on a pressure of 5 cmH₂O. CPAP can be raised in steps of 1 cmH₂O up to 10 cmH₂O. If this is not enough to maintain target oxygen saturation (SpO₂) from 89% to 92% in preterm infants <30 weeks GA and 90-94% in infants ≥30 weeks GA by pulse oximeter, FiO₂ will be added up to 0.40.

NHFOV: For Medin CNO, the initial NHFOV settings will be: mean airway pressure (MAP) of 6cmH₂O (range 6-10cmH₂O), frequency of 10 Hz (range 6-12), The Medin CNO has ten grades of amplitude. grade 7th amplitude will be to start with (grade range 7th-10th). For SLE 5000, The initial settings will be: MAP of 6 cm H₂O (range 6-10cmH₂O); frequency of 10Hz (range 6-12), inspiratory time 50% (1:1), oscillations of amplitude of 20 cm H₂O (range 20-35 cm H₂O). It is not strictly necessary to have visible chest oscillations, as most of the CO₂ elimination during NHFOV will occur in the upper airway dead space. Maximal allowed FiO₂ will be 0.40 and SpO₂ from 89% to 93% in

preterm infants <30 weeks GA and 90-94% in infants \geq 30 weeks GA by pulse oximeter.

Surfactant Therapy

Surfactant (Poractant alfa, Chiesi Pharmaceuticals, Parma, Italy) at dose of 200 mg/kg will be administered via INSURE method if infant presents with the following: infants \leq 26 week's gestation when FiO_2 requirement >0.30 and infants >26 week's gestation when FiO_2 requirement >0.40 [2]. Additional doses of surfactant may be given using INSURE technique at the discretion of the clinician.

Caffeine Therapy

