Caffeine (Caffeine Citrate Injection, Chiesi Pharmaceuticals, Parma, Italy) will be administered when infants present with moderate apnea (defined as 3 or more episodes in 24 hours or a single episode requiring resuscitation and bag-mask ventilation). The initial loading dose is 20mg/kg, and the maintenance dose is 5mg/kg per day.

Weaning from study interventions

The criteria for weaning noninvasive respiratory will be: (1) minimal or no signs of respiratory distress (RDS Silverman score < 5) ; (2) NHFOV MAP or NCPAP pressure <6 cmH₂O and (3) $FiO_2 < 0.25$ to achieve target SpO₂.

Criteria for intubation and IMV

These will be as follows [10-11]: (1)severe respiratory acidosis ($P_aCO_2 > 65$ mmHg with $pH < 7.20$);(2)severe apnea and bradycardia (defined as recurrent apnea with >3 episodes per hour associated with heart rate < 100 /min, a single episode of apnea that

requires bag and mask ventilation); (3) hypoxia ($FiO_2 > 0.5$ with $PaO_2 < 50$ mmHg), severe respiratory distress (RDS Silverman score > 7); (4) pulmonary hemorrhage; (5) pneumothorax; (6) cardiopulmonary arrest needing chest compressions.

Training

Since not all clinicians are well versed in all respiratory techniques and, particularly, NHFOV is a relatively new technique, the training is capital for the trial success. The protocol will be diffused between participating centers at least 3 months before the study begins. One investigator (YS) will explain the study protocol in an in-person meeting with all investigators. During the two months' period, clinicians will familiarize with the protocol and the respiratory techniques and the two co-principal investigators will be available to solve any doubt. A dedicated social media chat has been set to facilitate these exchanges. The trial is supposed to actually start in July 2017.

Outcomes

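### Below 30 weeks' gestation the SpO2 target differs by arm (89-92% on CPAP, 89-93% on NHFOV) with no reason given, and it feeds rules that both arms share

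*Combined protocol and SAP*

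**What the plan says.** The Ventilatory management section is written separately for each arm.

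- **CPAP.** The SpO2 target is "from 89% to 92% in preterm infants <30 weeks GA", and 90-94% from 30 weeks.
- **NHFOV.** The text reads "Maximal allowed FiO₂ will be 0.40 and SpO₂ from 89% to 93" per cent below 30 weeks, and again gives 90-94% from 30 weeks.

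Two later rules name no arm-specific target and apply to everyone.

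- **Surfactant Therapy.** Treatment is triggered in infants at or below "26 week's gestation when FiO_2 requirement >0.30", and in "infants >26 week's gestation when FiO_2 requirement >0.40".
- **Weaning from study interventions.** Besides minimal respiratory distress, the infant must have "NHFOV MAP or NCPAP pressure <6 cmH₂O and (3) $FiO_2 < 0.25$ to achieve target SpO₂".

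The pressure text also differs. On CPAP, "Neonates assigned to the CPAP group were initiated on a pressure of 5 cmH₂O", and then "CPAP can be raised in steps of 1 cmH₂O up to 10 cmH₂O. If this is not enough to maintain target oxygen saturation", FiO2 is added up to 0.40. NHFOV starts at a "mean airway pressure (MAP) of 6cmH₂O (range 6-10cmH₂O") with the same FiO2 maximum of 0.40, but the text does not say whether MAP or FiO2 is raised first.

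**The concern.** The surfactant and weaning rules look identical for the two arms, but each depends on the FiO2 needed to reach a target, and below 30 weeks the target is not the same. An infant held near the top of the range could need a different FiO2 under the two texts for a reason unrelated to the mode of support.

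The Outcomes section lists surfactant doses, duration of supplemental oxygen and duration of noninvasive ventilation as secondary outcomes. The protocol describes no masking of bedside staff, so each arm can be titrated to its own text. Randomisation and stratification by gestational age do not remove a difference that is created after allocation and by arm. At stake is the interpretation of these secondary outcomes: a difference between arms could partly reflect the oxygen target and not NHFOV itself.

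**Working it through.** The plan states no figure to reproduce here. The check sets the two arms' rules side by side.

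**Inputs** (Ventilatory management; strata from Randomization)

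| | CPAP | NHFOV | Difference |
|---|---|---|---|
| SpO2 floor, below 30 weeks | 89% | 89% | 0 |
| SpO2 ceiling, below 30 weeks | 92% | 93% | 93 - 92 = 1 point |
| Width, below 30 weeks | 92 - 89 = 3 | 93 - 89 = 4 | 1 point |
| Midpoint, below 30 weeks | (89 + 92)/2 = 90.5% | (89 + 93)/2 = 91.0% | 0.5 point |
| Target from 30 weeks | 90-94% | 90-94% | 0 |
| FiO2 maximum | 0.40 | 0.40 | 0 |

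**Where it applies.** The strata are 26+0 to 27+6, 28+0 to 29+6, 30+0 to 31+6 and 32+0 to 33+6 weeks. The first two lie below 30 weeks, so 2 of 4 are affected.

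**How it reaches the shared rules**

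1. If staff give only enough oxygen to reach the floor, both arms aim at 89% and the mismatch does nothing.
2. If staff aim for the middle of the range, the aim differs by 0.5 point. If they aim for the top, it differs by 1 point. In both cases the aim is higher on NHFOV.
3. With everything else equal, a higher aim cannot need less oxygen. In case 2 the mismatch can therefore bear on whether FiO2 passes the surfactant trigger and whether it falls below 0.25 for weaning.

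The protocol does not say where in the range staff should aim, so the documents do not choose between cases 1 and 2.

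**What cannot be computed.** The documents give no gestational-age distribution, no expected surfactant rate and nothing that links a 1-point change in ceiling to FiO2. Neither the number of infants affected nor the shift in any outcome can be derived.

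**The case against.** The strongest reply is that an FiO2 requirement ordinarily means the oxygen needed to bring the infant into range, so the common 89% floor governs and the mismatch never reaches the trigger. The 1-point gap may also be a typing slip; the protocol has others, such as the notation for the upper gestational-age limit. Much of this stands. It is why the effect is probably small. But these are the limits that staff are given, floor-seeking titration is not prescribed, and nothing elsewhere in the documents corrects or justifies the difference. If it is a slip, correcting it is easy; if it is intended, the reason should be stated.

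It can also be said that each mode needs its own rules. That is right for pressure, amplitude and frequency. It does not explain a saturation target, which is a goal for the infant and which the protocol already makes common from 30 weeks.

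A reader might go further in three ways that the documents do not support.

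- **The escalation wording biases surfactant use.** Only CPAP has a pressure-then-FiO2 sentence, but it is permissive. The missing order for NHFOV is largely missing detail within mode-specific settings, and the text does not settle in which arm the trigger would come first. Copying the CPAP sentence would still let the trigger be met at 5-10 cmH2O on CPAP and 6-10 on NHFOV. Raising MAP earlier is a clinical trade-off, with air leak and abdominal distention to watch.
- **The starting pressures should be equal.** The 5 and 6 cmH2O starts, and the ranges, are part of the two supports being compared.
- **The IMV result is compromised, or is safe.** Neither follows. With the size of any effect unknown, it cannot be called damaging, nor can it be dismissed against the planned difference of 56.4 - 24.3 = 32.1 points.

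**Conclusion.** The point holds in a limited form. The protocol sets an unexplained arm-specific oxygen target below 30 weeks: 1 point at the ceiling, 0.5 point at the midpoint, none at the floor, in 2 of 4 strata. It is a small, avoidable difference in co-intervention. It bears on the interpretation of oxygen exposure, duration of supplemental oxygen, surfactant use and weaning.

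This rests on two assumptions: that at least some staff titrate above 89%, and that they follow the target written for their arm. If neither is true, the consequence is nil and only an inconsistency in the text remains. The size of any effect on IMV is unknown. The absent MAP-versus-FiO2 order for NHFOV is a matter for clarification only.

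**What to change.** State one SpO2 target below 30 weeks in both Ventilatory management paragraphs, either 89-92% or 89-93%. Leave the target from 30 weeks, the FiO2 maximum, the surfactant thresholds and the mode-specific pressure settings as they are. If the sponsor intended different targets, the protocol should say so and give the reason.

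It would help to clarify separately how MAP and FiO2 are meant to be escalated on NHFOV; no particular order is recommended here.

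The cost is a short amendment and a notice to the 18 units, with no extra infants or visits. The downside is a 1-point change of ceiling in one arm: up on CPAP if 93% is chosen, down on NHFOV if 92% is chosen. The document is dated 13 July 2017, the start was planned for that month, and the Training section has the protocol circulated at least 3 months earlier. The change may therefore fall after enrolment has begun, in which case infants already enrolled should be analysed as randomised.

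### Below 30 weeks the SpO2 target differs by arm without a reason; secondarily, the NHFOV pressure range sits awkwardly with the weaning threshold of <6 cmH2O

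*Combined protocol and SAP*

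**What the plan says.** **Oxygen targets (Ventilatory management).** Below 30 weeks the SpO2 target is 89-92% in the CPAP paragraph and 89-93% in the NHFOV paragraph. From 30 weeks it is 90-94% in both. The FiO2 ceiling is 0.40 in both. No reason is given for the difference below 30 weeks.

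**Pressures (Ventilatory management).** For CPAP: "Neonates assigned to the CPAP group were initiated on a pressure of 5 cmH₂O", and "CPAP can be raised in steps of 1 cmH₂O up to 10 cmH₂O". For NHFOV on the Medin device: "mean airway pressure (MAP) of 6cmH₂O (range 6-10cmH₂O". On the SLE 5000: "The initial settings will be: MAP of 6 cm H₂O (range 6-10cmH₂O".

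**Weaning (Weaning from study interventions).** Three conditions must hold together: a Silverman score below 5, "NHFOV MAP or NCPAP pressure <6 cmH₂O", and FiO2 below 0.25 while reaching the SpO2 target.

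**Outcomes.** Days on supplemental oxygen and days on noninvasive ventilation are both listed as secondary outcomes. The primary outcome is need for invasive mechanical ventilation (IMV).

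**The concern.** The trial should compare two modes of support with everything else held equal. An SpO2 target is a rule for giving oxygen, and two of the quantities it governs are measured: days on oxygen directly, and days on noninvasive ventilation through the FiO2 condition for weaning. If the rule differs by arm, part of any difference in these outcomes comes from the rule and not from the mode of support. Statistical methods plans Student's t-test for continuous data, which cannot separate the two.

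The weaning pressure raises a similar question. The threshold is common to both arms, but the stated CPAP settings include a value that meets it and the stated NHFOV range does not. A site that reads the range literally would hold NHFOV infants on support for a reason unrelated to their condition.

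**Working it through.** There is no figure in the plan to reproduce, so the check sets the rules side by side.

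**1. SpO2 target by arm (from Ventilatory management)**

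| Gestational age | CPAP | NHFOV | Gap at lower limit | Gap at upper limit |
|---|---|---|---|---|
| Below 30 weeks | 89-92% | 89-93% | 89 − 89 = 0 | 93 − 92 = 1 point |
| 30 weeks or more | 90-94% | 90-94% | 0 | 0 |

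The band is 92 − 89 = 3 points wide on CPAP and 93 − 89 = 4 points wide on NHFOV. Of the four randomization strata, two lie wholly below 30 weeks (26-27 and 28-29 completed weeks). The plan sets no quota per stratum, so the share of the 300 infants affected is unknown.

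**2. What staff would do below 30 weeks if they follow the targets**

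- Below 89%: below target in both arms, so the same response.
- 89-92%: within target in both arms, so the same response.
- 93%: above target on CPAP, so oxygen is reduced; within target on NHFOV, so it need not be.
- Above 93%: above target in both arms, so the same response.

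Only the 93% reading separates the arms. There, the NHFOV infant may stay on a higher FiO2 for longer. That tends to lengthen days on oxygen and to delay reaching FiO2 below 0.25, so both effects run against NHFOV. Turning this into days would need the time infants spend at 93% and how closely staff titrate to target. The documents give neither.

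**3. Pressure settings against the weaning threshold of <6 cmH2O**

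- CPAP starts at 5, and 5 < 6, so the starting pressure meets the condition.
- NHFOV starts at 6 with a range of 6-10 on both devices. The lowest stated value is 6, and 6 is not < 6, so no value in the stated range meets it.

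Meeting the pressure condition does not by itself permit weaning; the Silverman and FiO2 conditions must hold too.

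**4. Is 6 a floor?** Three things suggest not. The range is given with the initial settings. The amplitude range also begins at its starting value and goes upward ("grade 7th amplitude will be to start with (grade range 7th-10th"). And a rule to wean when NHFOV MAP is below 6 presupposes that MAP can get there. Against this, the frequency range in the same paragraph (start 10 Hz, range 6-12) extends both ways from its start, so a range there does not always mean upward only. No section says that MAP may go below 6.

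**5. Link to the primary outcome.** The intubation criteria (blood gas acidosis, apnea with bradycardia, hypoxia defined by FiO2 and PaO2, Silverman score, pulmonary hemorrhage, pneumothorax, arrest) are common to both arms. None uses an SpO2 target or the weaning pressure.

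**The case against.** **On oxygen.** Whether an infant can reach target at FiO2 below 0.25 turns on the lower limit, which is 89% in both arms. The upper limit may be a typing slip, and a 1-point gap is small. The first part limits the effect on weaning but does not remove it: the upper limit decides when oxygen is turned down, and FiO2 has to come down before the condition is met. A slip would still be the rule that sites are asked to follow.

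**On pressure.** A reader might infer that NHFOV infants cannot be weaned under this protocol. The documents do not support that. The range belongs to the initial settings, nothing calls 6 a minimum, and the weaning rule itself names NHFOV MAP below 6. Nor is the silence special to NHFOV: the plan says how CPAP is raised, but gives no step-down rule and no CPAP minimum. These points stand, and they make this the lesser half of the concern.

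**On clarification.** Training provides an in-person meeting, and "the two co-principal investigators will be available to solve any doubt". That makes it unlikely that many sites would adopt an unworkable floor. It does not put the rule in writing, and the same section says that clinicians' experience varies and that NHFOV is relatively new.

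**On direction.** Any bias in these duration outcomes runs against NHFOV, so it could hide a benefit there but not create one. This stands.

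**Conclusion.** The SpO2 difference is real on the text: 1 point at the upper limit, below 30 weeks only, in two of four strata, with no reason given. It can bias days on supplemental oxygen, and less so weaning, against NHFOV. This assumes that staff titrate oxygen to the written target. The size cannot be computed from the documents.

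The pressure wording conflicts on its face with the weaning threshold. The probable intent is that MAP may be lowered below 6; if every site does so, the threshold is common and little bias remains. If any site treats 6 as a floor, days on noninvasive ventilation is biased against NHFOV, again by an unknown amount.

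A reader might also infer that the primary comparison is affected. Nothing in the plan shows this, because the criteria for intubation and IMV are the same in both arms and refer to neither rule. Severity is minor.

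**What to change.** 1. Use one SpO2 target below 30 weeks in both arms, either 89-92% or 89-93%. What matters for the comparison is that it is common.
2. Keep the weaning threshold at <6 cmH2O and state that NHFOV MAP may be lowered to 5 cmH2O for weaning.

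The cost is a short amendment (one number and one sentence) and a note to the 18 sites. Sample size and analyses do not change.
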